PLEASE NOTE: Subjects continued participation in the study after this point will depend on the results of the vital signs, waist measure as well as blood sugar and lipid results. Further, if subjects are a woman who is able to bear a child, subjects will have a pregnancy test that must be negative in order to participate – this will be determined via urine collected at the screening.

Screening Visit 2 at the Clinical Research Center (CRC) or IFNH or Foran Hall (will last about 1-2 hours)

IMPORTANT: Subjects must fast (not eat, water ok) for 4-10 hours before this visit. During the second screening visit the following assessments will take place at the CRC or IFNH or Foran Hall:

- Review of your medical history
- Physical exam and vital signs (blood pressure, heart rate) will be conducted.
- Resting electrocardiogram (ECG) to see the electrical activity of your heart will also be done.

If subjects continue to qualify for the study the remainder of the visit will involve the study procedures described below:

A. Body Composition and Resting Metabolism:

- Subjects must be fasting for at least 4-10 hours before this procedure.
- Subjects weight will be measured without shoes and while wearing minimal clothing.
- Subjects waist and hip circumference ratio will be obtained with a tape measure to determine how much fat is located in the central part of your body.

12/31/2499

- The total amount of fat and muscle in the subjects body will be measured via DEXA in Foran Hall.
- Subjects will be required to wear clothes without metal on them (including zippers and bras with an underwire). If their clothes have metal, we will ask that them to change into a pair of shorts and a t-shirt or wear a hospital gown provided by the lab.
- If there are technical issues with the DEXA machine, we will measure the total amount of fat and muscle in the subjects body with the BodPod® in the IFNH.
 - We will provide a swimsuit and swim cap for subjects to wear during this procedure to help standardize your results. The swimsuit and swim cap are provided to get accurate results. Subjects will not get wet at any time during this measurement. Subjects will enter the device and sit down. A door will close while they sit in the BodPod®. Subjects are asked to breath normal and be still. The BodPod® looks like a large white egg and has a window on the door.

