LoEx + Metformin: If subjects are assigned to this group, subjects will participate in the same LoEx exercise program as outlined above. But here you will be provided metformin. Metformin is a common medication routinely used to treat high blood sugar and has secondary effects on vascular health. Subjects will not be able to find out if they are on metformin until the study is done. If the subjects doctor needs to know whether metformin or placebo pill is prescribed due to medical reasons that directly affect the subjects medical treatment, the people doing this study can find out.

HiEx + Metformin: If subjects are assigned to this group, subjects will participate in the same HiEx exercise program and receive metformin as outlined above.

PHASE 4: POST INTERVENTION TESTING (Visits 54-56)

After the 16 week intervention subjects will be asked to undergo the same series of testing that they completed in phase 2. Subjects cannot drink alcohol or take medications/supplements 24 hours prior to testing unless approved by the study team. In addition, subjects cannot eat or drink foods that contain caffeine 24 hours prior to testing. We also ask that subjects refrain from any structured exercise for 24 hours prior to testing and limit exercise to your normal everyday activities. All study testing visits highlighted above in Visits 2, 3 and 4 (Body Composition, Fitness, AI, PWV, OGTT, etc.) will be repeated (except physical screening and resting ECG). The order of the tests post-intervention will be:

- 1. Clamp Study (Visit 54)
- 2. OGTT (Visit 55)
- 3. Body Composition and Fitness (Visit 56)

Visits 53, 54 and 55 will be on consecutive days (i.e. 1 day apart).

*Intervention (medication and exercise) may be extended or shortened by approximately one week if scheduling requires to complete visits 54 and 55 of post-intervention testing.

PHASE 5: Unsupervised Exercise Follow-up (Visit 57-58)

12/31/2499

After the post-intervention testing, subjects will be asked to exercise on their own (e.g. purchase a gym membership, etc.) while wearing the polar activity tracker watch and heart rate strap. We ask that subjects exercise at the same intensity that you have been exercising with us during the intervention. We will check in by phone within week 2 to see if they are exercising, or if there are any complications.

Visit 57 approximately 30 min

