 - Subjects will be required to wear clothes without metal on them (including zippers and bras with an underwire). If clothes have metal, we will ask that subjects change into a pair of shorts and a t-shirt or wear a lab hospital gown.
 - If there are technical issues with the DEXA machine we will measure the total amount of fat and muscle in the subjects body with the BodPod® in the IFNH.
 - We will provide a swimsuit and swim cap for subjects to wear during this procedure to help standardize the results. The swimsuit and swim cap are provided to get accurate results. Subjects will not get wet at any time during this test. Subjects will enter the device and sit down. A door will close while the subject sits in the BodPod®. They are asked to breath normal and be still. The BodPod® looks like a large white egg with a window on the door.

NOTE: in the event of scheduling conflicts, cardiovascular fitness and/or body composition assessments may be completed within 1 week of doing the OGTT during Visit 58.

END OF STUDY:

After subjects have completed Phase 5, the study will be complete.

B. Data Points

We are collecting blood and urine during experimental visits. Vital signs, including blood pressure, temperature, heart rate, as well as aerobic fitness, body composition, resting metabolism, non-exercise physical activity, appetite, as well as quality of life. Please see the study overview (Study Duration) that outlines when outcomes will be collected.

C. Study Duration

Subjects participation in this study will require about **58** study visits over about 7-8 months. Each visit will last between **1-6** hours depending on whether it is for research purposes (e.g. about 3-6 hours) or exercise training (e.g. 1-1.5 hours). There are 2 Screening Visits and 5 Test Visits. Thus, the majority of visits include exercise training (48 visits).

D. Endpoints

The primary outcome for this study will be changes of basal FMD before the insulin clamp pre and post intervention. We will also examine the influence of insulin on FMD as well as metabolic insulin sensitivity, defined as the glucose infusion during the last approximate 30 minutes of the clamp procedure. Together, these findings will help tease out vasculature vs. metabolic insulin sensitivity differences between treatments. Correlations will be conducted to understand the relationship between endothelial function and metabolic insulin sensitivity with substrate oxidation,

12/31/2499

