1.6 Study Variables

A. Independent Variables, Interventions, or Predictor Variables

This is a randomized by sex, double-blind, placebo controlled trial. A placebo is needed to minimize potential behavioral changes with pharmacological intervention. This will isolate the effects of exercise intensity based training on respective outcomes. As a result, exercise at low or high intensity with placebo will serve as standard of care/control, while exercise at low or high intensity with metformin will be the experimental conditions. Pre and post test data will be compared statistically.

Data will be analyzed using R (Vienna, Austria, 2011). A two-way repeated measures analysis of variance (ANOVA) will be used to assess time course differences (group x test). Bonferonni post-hoc analysis will be used to determine group differences and paired t-tests will be used to assess within treatment effects. Linear regression analyses will be used to identify relationships between respective variables. A *P*<0.05 will be considered statistically significant. Data will be expressed as mean ± SEM.

12/31/2499

The same statistical approach for secondary analysis will be conducted as the primary variable analysis.

B. Dependent Variables or Outcome Measures

- 1. Insulin Sensitivity
- 2. Fitness (e.g. VO2max, physical activity amount, heart rate, RPE, etc.)
- 3. Body composition (e.g. weight, fat, FFM, BMD, waist circumference, etc.)
- 4. Vascular Function (e.g. FMD, CEU, heart, arterial stiffness, etc.)
- 5. Questionnaires (e.g. Sleep, activity, quality of life, hunger, etc.)
- 6. Glucose (e.g. substrate, isotope)
- 7. Lipid Profile (e.g. TG. HDL. FFA. etc.)
- 8. Blood clinical chemistries (e.g. CBC)
- 9. C-peptide
- 10. Insulin
- 11. Inflammation (e.g. endothelin-1, adiponectin, Microparticles, etc.)
- 12. Nitrates
- 13. Gut hormones (e.g. ghrelin, GLP-1, etc.)
- 14. Pregnancy (in females), blood for screening at each admission.
- 15. Energy metabolism (e.g. rest, exercise, insulin-stimulation).
- 16. Gut microbiota
- 17. Cognitive measures using NIH toolbox

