1.10 Timetable/Schedule of Events

Study Screening and Testing Schedule Visit Overview.

Study Visit	Screening Visit 1	Screening Visit 2	Pre- Test OGTT Visit 3 or 4	Pre- Test Clamp Visit 3 or 4	Exercise Training (Intervention Period) 5 d/wk* Visits 5-53	Post- Intervention Clamp Testing Visit 54	Post- Intervention OGTT Testing Visit 55-56	Follow up Week 4 check- in Visit 57	Follow up Week 8 OGTT Testing Visit 58
Informed Consent	X								
Blood Draw	X		X	Χ		X	X		х
History and Physical		X							
Urine Collection			X	X		X	X		X
VO2peak (Treadmill testing)		X					X		X
Body Fat measurement (Waist and Hip circumference,		X					Х		X

12/31/1799

12/31/2499

Approval Date:

DEXA or Bod Pod)								
Indirect Calorimetry	Х	·	X		X			X
Exercise* Indirect Calorimetry				X*	X			
24 hour Blood Pressure		Х		X*				
Blood Pressure, AI, CEU and PWV tests			X		X			X
FMD, CCA-IMT		Χ	Χ		X		-	Χ
Muscle/Fat Biopsy		·	Х		X			
Diet Record	X			Χ		X	Х	Χ
Appetite Questions		Х		X		X		Х
Quality of Life Questions		Х				X		Х
NIH Toolbox		Χ				Х		Χ
Accelerometer	X			Χ	_		Х	Х
Heart Rate Monitors				Χ			x	

Exercise Training will be performed at Loree Gymnasium or IFNH on Cook-Douglas Campus 3 days/week and supervised by an exercise physiologist/research team member. The other 2 days will be non-supervised as you will be asked to wear a heart rate monitor. Accelerometers will be provided for weeks 0, 8, 16, 20, 24. *Exercise Indirect calorimetry will include measures of breath samples the first day of training and within the last weeks of training.

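### The BodPod fallback is triggered visit by visit, so some fat and fat-free-mass changes can mix a device difference with true change

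*Combined protocol and SAP*

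**What the plan says.** Section 1.3, Screening Visit 2, part A sets the default: "The total amount of fat and muscle in the subjects body will be measured via DEXA in Foran Hall". A fallback to the BodPod follows: "If there are technical issues with the DEXA machine, we will measure the total amount of fat and muscle in the subjects body".

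For the post-intervention assessment, Phase 4 of section 1.3 says: "All study testing visits highlighted above in Visits 2, 3 and 4 (Body Composition, Fitness, AI, PWV, OGTT, etc.) will be repeated". Body composition falls at Visit 56. No device rule is added there, so the Visit 2 procedure applies with its fallback.

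For Visit 58, part C restates the fallback without reference to the device used earlier: "If there are technical issues with the DEXA machine we will measure the total amount of fat and muscle". A note allows some flexibility when schedules conflict: "cardiovascular fitness and/or body composition assessments may be completed within 1 week of doing the OGTT during Visit 58". The schedule in section 1.10 lists the devices as alternatives in a single row: "DEXA or Bod Pod".

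Section 1.6 B lists the outcome as "Body composition (e.g. weight, fat, FFM, BMD, waist circumference, etc". Section 1.6 A analyses secondary outcomes in the same way as the primary one: a group-by-test repeated-measures ANOVA, Bonferroni post-hoc comparisons and within-arm paired t-tests. Section 1.3 D adds correlations of endothelial function and insulin sensitivity with body composition, among other variables.

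**The concern.** The device depends on whether the DEXA works on the day, not on what the participant had before. Section 4.7 A describes BodPod as air displacement and DEXA as a radiation-based measurement. If the two give different values for the same person, a change from one to the other contains that difference as well as any real change.

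The plan takes care to standardise conditions within each device (fasting, clothing without metal, a supplied swimsuit and cap) but leaves the device itself free to change between visits. A device offset would look like fat loss or gain in the paired comparisons and would add error to the body-composition correlations. The fallback wording also covers only fat and muscle, while bone mineral density is a listed outcome. A BodPod visit therefore has no stated source for bone mineral density.

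**Working it through.** **Is the path open?** Body composition is measured three times.

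| Visit | Default | Fallback | Tied to the earlier device? |
|---|---|---|---|
| 2 (baseline) | DEXA | BodPod if DEXA has a fault | not applicable |
| 56 (post) | as Visit 2 | as Visit 2 | no |
| 58 (follow-up) | DEXA | BodPod if DEXA has a fault | no |

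A fault at Visit 2 alone mixes both changes from baseline. A fault at Visit 56 alone mixes the pre-post change, which is the one the analysis in section 1.6 A compares. A fault at Visit 58 alone mixes the follow-up change. The documents contain no same-device requirement, cross-calibration, instruction to record the device, device term in the model, or rule for mixed pairs.

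**How large could it be?** The plan states no figure to reproduce. The arm size of 15 is from section 1.5. Everything else below is an assumption.

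*Shift in an arm's mean change.* With k mixed pairs, all in the same direction, and device offset b in percentage points of body fat:

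shift = (k / 15) × b

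- k = 1: 1/15 × 1 = 0.07 and 1/15 × 4 = 0.27 points
- k = 3: 3/15 × 1 = 0.2 and 3/15 × 4 = 0.8 points

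Switches in opposite directions cancel, so k is the net count.

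*Effect on the within-arm paired t-test.* Let a share s of the arm switch in one direction. The mean change shifts by s × b, and the SD of change becomes √(SD² + b² × s × (1 − s)). Take b = 2, SD = 2, s = 0.2 (3 of 15) and no true change:

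- shift = 0.2 × 2 = 0.4 points
- SD of change = √(4 + 4 × 0.16) = √4.64 = 2.15, an increase of 7.7%
- noncentrality = 0.4 / (2.15 / √15) = 0.72
- false-positive rate from the noncentral t distribution with 14 df = about 10%, against a nominal 5%

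Over b of 1 to 3, SD of 2 to 3 and s of 10% to 30%, with 15 per arm, the shift is 0.1 to 0.9 points, the SD of change grows by 0.5% to 21%, and the false-positive rate is about 5% to 27%.

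*Effect between arms.* If switching is equally common in all arms, the shift s × b is the same in each and cancels from the expected difference. The larger SD remains, as does whatever imbalance arises by chance.

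*Scale.* Section 1.5 is designed to detect 4.2 / 3.4 = 1.24 SD between arms. At an assumed SD of 2 points of body fat, that is about 2.5 points. One mixed pair is 0.07/2.5 to 0.27/2.5, about 3% to 11% of that. Three at the largest offset are 0.8/2.5, about a third.

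**The case against.** BodPod is a contingency, not a routine choice. DEXA is the default, the documents do not say how often it fails, and they do not show that any mixed pair has occurred. Body composition does not appear in the hypotheses of section 1.1 and is one of 17 outcome categories. The device offset and SD are assumed, and the shifts above require a net excess of switches in one direction. All of this stands, and it limits the weight of the point. It does not close the gap: when the fallback is used, the plan neither prevents a mixed pair nor says how to analyse one.

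A reader might infer that a treatment comparison could show a device difference instead of a treatment effect. The documents do not support this. The trigger is a machine fault, which has no evident link to the randomised arm, so the expected between-arm bias is about zero. A reader might also suppose that outages come in blocks and so cluster the mixed pairs. That is plausible, but nothing in the documents says so.

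Deleting mixed pairs outright is also open to objection in arms of 15 to 20, since a complete-case repeated-measures ANOVA could lose the whole participant. That is a reason to keep them in a sensitivity analysis.

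**Conclusion.** The point holds as a cheap improvement to a secondary measure. As written, the fallback allows fat and fat-free-mass changes to be computed across two devices at any of the three time points, and nothing in the analysis accounts for it. The consequences are distorted within-arm paired changes, distorted body-composition correlations, extra noise and possible chance imbalance between arms. No systematic between-arm bias is expected. Weight, waist, the primary outcome and its sample size are untouched.

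The existence of the gap is clear from the text; its size is not. The illustrative shift of 0.07 to 0.8 points rests on assumed offsets of 1 to 4 points and one to three mixed pairs in the same direction. If the devices agree closely, or the DEXA rarely fails, the effect is negligible.

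**What to change.** Amend section 1.3 (Screening Visit 2 part A, Phase 4, and Visit 58 part C) and the schedule in section 1.10 to say:

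- Each participant is measured on the same device at Visits 2, 56 and 58. If the baseline scan was by BodPod, BodPod is used throughout.
- If the DEXA is down at a follow-up visit for a participant with a DEXA baseline, the scan is rescheduled within about 1 week. Visit 58 already has this window for scheduling conflicts; extend it to machine faults and to Visit 56.
- The device is recorded at every scan.

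Add to section 1.6 A: changes in fat and fat-free mass are analysed in same-device pairs, with mixed pairs included as a sensitivity analysis. Change in bone mineral density uses DEXA pairs only.

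The cost is a short amendment, an occasional rescheduled scan, and a few pairs left out of the same-device analysis. A deferred Visit 56 scan may fall a few days into the unsupervised phase, which makes that end-of-intervention value slightly less clean. Phase 4 requires only Visits 53 to 55 to be on consecutive days, so moving the Visit 56 scan breaks no stated timing rule.

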Euglycemic-Hyperinsulinemic Clamp (approximately 6 hours)

- Subjects will arrive at the CRC fasted for about 10 hours, and we will put two intravenous catheters (IV) into two vein in the subjects arm and obtain baseline blood samples.
- During this visit, we will perform the 2-hour euglycemic-hyperinsulinemic clamp or "clamp" study. This test is the gold standard for measuring sensitivity to insulin.
- Since the clamp study can be significantly enhanced by the use of glucose tracers, we will inject a glucose labeled with tracer (~2 drops) called dideuterated glucose (Dideuterated glucose is non-radioactive). The tracer contains a very small amount of heavy hydrogen (²H₂), which makes the glucose more identifiable. A small percentage of heavy hydrogen is naturally present in your body (0.015%). What we do is add to this natural pool and measure its concentration in the blood. This allows us to determine how insulin is controlling your rate of liver glucose production vs. skeletal muscle glucose uptake. The infusion of dideuterated glucose through the IV is continued during an entire 4-hour period (2 hour before the clamp and 2 hour for the clamp, i.e. about 4 hour total).
- Subjects will not eat, drink, or take any medications/vitamins on the morning of the test.
- Subjects will be given a meal once the "clamp" study is complete.
- Insulin will be infused at a constant rate to maintain the blood concentration at approximately 100 μU/ml. Subjects blood sugar concentration will be measured every 5 minutes and infused at a variable rate to maintain a normal blood sugar level (90 mg/dl). Blood draws for insulin will occur every 30 minutes up to 90 minutes, and then every 10 minutes until the end of the clamp.
- Subjects will also have a see-through canopy (cover) over their head before and at the end of the clamp. This procedure uses the same machine used during exercise in screening visit 2, part B above. This device allows us to measure how much sugar and fat you are using to create energy. Also, by measuring and analyzing the oxygen and carbon dioxide levels in the subjects breath it is possible to estimate if subjects are storing glucose as glycogen.

Urine Collection:

• Subjects will be provided with a plastic container and asked to collect one urine void on visit 3 and 4. The amount and time of subjects urine collection will be recorded and analyzed for nitrogen, protein and metabolites.

Blood flow to be done at Visit 3 and/or 4, 54 and 58:

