4.0 Subject Considerations

4.1 Subject Selection and Enrollment Considerations

A. Method to Identify Potential Subjects

Prospective subjects will be recruited through posted and/or mailed flyers. Please see attached flyer that will be included in newspapers, Instagram, Reddit, Facebook or twitter as well as mailings via coldcontacts. Cold-contacts may be iniatited via use of electronic medical records using inclusion/exclusioncriteria through the Rutgers Robert Wood Johnson Medical School Endocrinology/Cardiology platforms (connected with [name] and [name]). Additionally, ResearchMatch.org will be utilized as a recruitment tool for this protocol. ResearchMatch.org is a national electronic, web-based recruitment tool that was created through the Clinical & Translational Science Awards Consortium in 2009 and is maintained at Vanderbilt University as an IRB-approved data repository (see IRB #090207). We will also use Trialfacts, a specialized patient recruitment service that combines extensive marketing and advertising expertise with in-depth clinical trial experience in order to aid research groups in successful study recruitment. Trialfacts uses digital advertising and specialized targeted ads based on eligibility criteria and online questionnaire data collection with specific software.

B. Recruitment Details

Prospective participants will be recruited using listservs and flyers across Rutgers University campus as well the Rutgers Robert Wood Johnson Medical School ([name].

We will also place flyers IRB approved in the New Brunswick and surrounding community at participating stores/libraries/etc. Newspapers (e.g. New Brunswick Today) and social media (Twitter, Facebook) will also be contacted about placing the flyer as an insert or respective info. Interested individuals will be asked to contact the research team by phone to get a more detailed description of the study. Prospective participants will be scheduled for a screening visit to establish eligibility. Enrollment will be decided after chemistry panel, blood pressure and waist circumference results are confirmed for group assignment. This will be evaluated by the PI, study physician and research team.

C. Subject Screening

Inclusion Criteria for Subjects

- Male or female >40 and <80 years old.
- Has a body mass index >25 and <47 kg/m².
- Not diagnosed with Type 2 diabetes.
- Not currently engaged in > 150 min/wk of exercise

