- At minimum, subject will have abdominal obesity (increased waist circumference as defined below) and may have any additional National Cholesterol Education Adult Treatment Panel III Metabolic Syndrome criteria:
 - o Increased waist circumference (≥102 cm in men; ≥88 cm in women)

12/31/2499

- Elevated triglycerides (≥150 mg/dl), or on medication for treating the condition
- Reduced HDL-cholesterol (<40mg/dl in men, <50 mg/dl in women), or on medication for treating the condition
- o High blood pressure (≥130 mmHg systolic or ≥85mmHg diastolic), or on medication for treating the condition
- Elevated fasting glucose (≥100 mg/dl), or on medication for treating the condition
- Other major risk factors to be noted based on the Framingham Risk Score
 - HbA1c 5.7-6.4%
 - LDL > 130 mg/dL
 - Family history of type 2 diabetes (immediate family, i.e. parent/sibling)
 - History of gestational diabetes
 - History of Polycystic Ovarian Syndrome
 - Family history of pre-mature cardiovascular disease (immediate family i.e. parent/sibling) before 55 for males or 65 for females that can include heart attack, peripheral arterial disease, abdominal aortic aneurysm, symptomatic carotid artery disease or clinical coronary heart disease)
 - Age (> 45 years old for men; > 55 years old for women)
 - Black/African American, Mexican, Asian, and/or Hispanic
- Subjects currently taking medications that affect heart rate and rhythm (i.e. Ca++ channel blockers, nitrates, alpha- or beta-blockers)

Exclusion Criteria for Subjects

- Morbidly obese patients (BMI >47 kg/m²) and overweight/lean patients (BMI <25 kg/m²)
- Evidence of type 1 diabetes and diabetics requiring insulin therapy.
- Subjects who have not been weight stable (>2 kg weight change in past 3 months)
- Subjects who have been recently active (>30 min of moderate/high intensity exercise, 2 times/week).
- Subjects who are smokers or who have guit smoking <5 years ago
- Subjects prescribed metformin or have taken metformin within 1 year.
- Subjects with abnormal estimated glomerular filtration rate (eGFR).
- Hypertriglyceridemic (>400 mg/dl) and hypercholesterolemic (>260 mg/dl) subjects
- Hypertensive (>160/100 mmHg)
- Subjects with a history of significant metabolic, cardiac, congestive heart failure, cerebrovascular, hematological, pulmonary, gastrointestinal, liver, renal, or endocrine disease or cancer that in the investigator's opinion would interfere with or alter the outcome measures, or impact subject safety.

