Definity Microbubbles side effects include: headache, back and chest pain, flushing, dizziness, a metallic taste, vomiting, coughing, and dry mouth. The FDA has issued a black box warning for Definity (a type of warning that appears on the package insert for certain drugs that may cause serious harmful effects) for cardiopulmonary and hypersensitivity reactions. There have been convulsions, arrhythmias, respiratory distress, and death noted in patients with an intracardiac or intrapulmonary shunt so the FDA has suggested using it with extreme caution in patients with known cardiac or cardiopulmonary disease. We will not have any of these types of subjects in our study but should an emergency arise we will have trained personnel and resuscitation equipment available. We have been using Definity in subjects with obesity for over 4 years (~ 100 subjects) and we have had 0 adverse events. Thus, these occur rarely.

Insulin infusion: There is a potential for hypoglycemia (not very often). The doses of insulin used during the euglycemic insulin clamp are low and the blood glucose level will be monitored every five minutes throughout the insulin infusion. The glucose infusion will be adjusted to maintain the subject's glucose level within 10% of normal fasting. This occurs infrequently.

Body composition: Air displacement determination of body composition by Bod Pod may cause anxiety and /or claustrophobia. The DXA measurements will produce a small amount of radiation which is less than that received during two days of background radiation.

12/31/2499

A subject may incur lost wages from his/her job due to time spent at the screening and/or experimental visits. There is also the possibility, though low, for breach of confidentiality with using an outside company, Greenphire, to distribute the ClinCard compensation.

Risk of Harm from an Intervention on a Subject with an Existing Condition

We expect our subjects to be generally healthy and should not have any severe or decompensated medical conditions. Exclusion criteria and physicals performed should minimize any risks and the exercise/metformin treatment should not bring harm.

Other Foreseeable Risks of Harm

We do not anticipate any other foreseeable risks given the scope and duration of the study.

 Observation and Sensitive Information NA

B. Procedures which Risk Harm to Embryo, Fetus, and/or Pregnant Subjects

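### Metabolic insulin sensitivity is taken as an uncorrected clamp infusion rate although a 10% glucose band is tolerated, and the clamp target is worded in two ways that need reconciling

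*Combined protocol and SAP*

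**What the plan says.** The clamp procedure in Section 1.3 A gives a numeric target: glucose is "infused at a variable rate to maintain a normal blood sugar level (90 mg/dl"). Insulin is held constant ("Insulin will be infused at a constant rate to maintain the blood concentration at approximately 100" μU/ml), and glucose is sampled often: "Subjects blood sugar concentration will be measured every 5 minutes".

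The insulin-infusion paragraph of Section 4.7 A describes the same control differently: "The glucose infusion will be adjusted to maintain the subject's glucose level within 10% of normal fasting". No section says what the last two words of that sentence refer to or ties them to 90 mg/dl.

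Section 1.3 D makes metabolic insulin sensitivity an outcome, "defined as the glucose infusion during the last approximate 30 minutes of the clamp procedure". It does not mention the glucose level reached or whether glucose was steady. The analysis text in Section 1.6 A (repeated-measures ANOVA, post-hoc comparisons, paired t-tests, regression) adds no correction, and Section 6.1 supplies none.

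On population, Section 4.1 C requires abdominal obesity and lists "Elevated fasting glucose (≥100 mg/dl), or on medication for treating the condition" among further features that participants may have. On diabetes status the inclusion list says "Not diagnosed with Type 2 diabetes".

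**The concern.** There are two separate issues.

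First, the two descriptions of the target can be read as the same rule or as different rules. If the second means the participant's own fasting level, the target is no longer one number. It varies between participants, and within a participant it could change between the baseline clamp and Visit 54.

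Second, whichever reading is meant, glucose may move within a 10% band. The infusion rate equals glucose disposal only when the amount of glucose in the body is constant. If glucose is rising during the window, part of the infusion is filling the pool and the rate overstates uptake. If it is falling, the rate understates uptake. The endpoint definition makes no allowance for this.

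Metabolic insulin sensitivity is not the primary outcome, but it is named in the overarching hypothesis in Section 1.1 B. Section 1.3 D relies on it to separate vascular from metabolic effects of the treatments, and it enters the planned correlations.

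**Working it through.** **Inputs from the protocol.** Target 90 mg/dl and glucose sampling every 5 minutes (Section 1.3 A); 10% tolerance (Section 4.7 A); window of about 30 minutes (Section 1.3 D); possible fasting glucose of 100 mg/dl or more (Section 4.1 C).

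**Assumptions not in the protocol.** Glucose space V of 1.9-2.5 dl/kg; infusion rate of 3-6 mg/kg/min; dependence of uptake on glucose at fixed insulin anywhere from none to fully proportional.

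Section 1.5 gives power for FMD only, so there is no planned figure for the clamp outcome to reproduce or to compare these errors with.

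**1. Tolerance read as a general normal level of 90 mg/dl.**

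- 90 × 0.9 = 81 and 90 × 1.1 = 99.
- The band is 81-99 mg/dl and contains 90, so the two sections agree.

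**2. Tolerance read as the participant's own fasting value F.**

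- 90 lies in the band only if 0.9F ≤ 90 ≤ 1.1F. That gives F ≤ 90/0.9 = 100 and F ≥ 90/1.1 = 81.8 mg/dl.
- F = 100: band 90-110 (90 is just at the edge).
- F = 105: band 94.5-115.5 (90 excluded).
- F = 115: band 103.5-126.5 (wholly above 90, and above 99).

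If this target were also reset at the post clamp, an illustrative fall in F from 110 to 100 would change the rate at unchanged sensitivity by 100/110 − 1 = −9.1% under full proportionality, by half of that (−4.5%) under half proportionality, and by 0 under none.

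**3. Drift within the window, on either reading.**

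Leaving aside any remaining liver output, which the tracer is meant to measure:

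uptake = infusion rate − V × (change in glucose)/(length of window)

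Take a steady change of 9 mg/dl (10% of 90) over 30 minutes, that is, from target to the edge of the band or back:

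- V = 1.9: 1.9 × 9/30 = 0.57 mg/kg/min.
- V = 2.5: 2.5 × 9/30 = 0.75 mg/kg/min.
- Relative to the assumed rates: 0.57/6 = 9.5% up to 0.75/3 = 25%.
- A drift of 3 mg/dl gives a third of this: 0.19-0.25 mg/kg/min. No drift gives zero.

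The error in a pre-post change is the difference between the two visits' terms, so equal drift in the same direction cancels.

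**4. Level within the band.**

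Two steady clamps at opposite edges, 81 and 99 mg/dl, could differ in rate by 99/81 − 1 = 22% under full proportionality and by 0 under none. A pool correction does not remove this, but reporting mean glucose makes it visible.

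**The case against.** **The wording need not conflict.** Section 1.3 already calls 90 mg/dl a normal level, so the phrase in Section 4.7 reads naturally as a tolerance around it. Section 1.3 is the procedure, whereas Section 4.7 is a risk paragraph about hypoglycemia. This stands: a reader might infer a flat contradiction, but the text supports only an undefined term with two possible readings.

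**The fasting-glucose bias is conditional.** A reader might infer that the infusion rate tracks fasting glucose, so that a metformin effect on fasting glucose would imitate the blunting the trial is looking for. That needs the own-fasting reading, a target reset at the post clamp, and a difference between arms in the fall of fasting glucose. The protocol establishes none of these. With a fixed 90 mg/dl this route closes. Elevated fasting glucose is also optional for entry, so the share of participants affected is unknown.

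**Operators will be consistent.** Section 2.2 requires training and investigator sign-off, and the laboratory protocols are not part of the document. That is a fair reason not to assume that staff apply different rules. It does not supply the missing definition.

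**Drift will be small and mostly noise.** Five-minute readings and a variable infusion are meant to keep glucose steady, drift can go either way, and metformin versus placebo is double-blind. This is largely right, and it is why the drift figures are bounds and not expected errors. It does not justify leaving the rate uncorrected when the values needed are already collected.

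**The endpoint sentence is only a summary.** True, but it is the only definition in the document, and as written it is the raw infusion.

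**Conclusion.** The point holds in a limited form and is a cheap improvement. The clamp target is described in two ways that agree on one reading and diverge on the other, and the protocol does not say which is meant. Independently of that, the metabolic insulin sensitivity endpoint is an uncorrected rate under a tolerated 10% glucose band.

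For a clamp that is on target at one end of the window, drift inside the band misstates uptake by at most 0.57-0.75 mg/kg/min. This rests on an assumed glucose space of 1.9-2.5 dl/kg and a steady drift over the whole window. The expected error is smaller and may be near zero in a steady clamp.

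The consequence is confined to the clamp-derived metabolic insulin sensitivity outcome and its correlations. It would be wrong to infer that every treatment contrast is affected: basal FMD is measured before the clamp, and the OGTT, fitness and body-composition outcomes do not use clamp glucose.

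**What to change.** - Reconcile Sections 1.3 A and 4.7 A so that the clamp target and its tolerance are stated once and in the same terms. Which target applies is for the investigators to say; this point takes no position on it.
- In Section 1.3 D, define metabolic insulin sensitivity as the infusion rate over the last 30 minutes minus V × (change in glucose)/(length of window). Use the 5-minute glucose values and a single glucose-space constant V fixed in advance.
- Report mean glucose in that window by arm and visit, so that any difference in the level reached can be seen.

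The cost is one reconciled sentence, one line in the endpoint calculation and a little more data handling. No new sampling is needed. The correction brings in one assumed constant, which should be stated with the result.
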